### **16.5. Sample Size Considerations**

Data for estimating the sample size were derived from studies reporting the distribution (mean value and standard deviation) of the TSQM-9 in MS patients treated with IFN (9). Assuming an average value of the overall convenience domain at baseline of 55 (SD=16) (9), with 250 subjects we have a power of 90% to detect a change of 3 points on the overall convenience domain (from 55 to 58) under the conservative hypothesis of a SD=16 (9) for the difference between baseline and week 12. However, by assuming a drop-out rate up to 10% during the study, we consider it appropriate to enrol a total of 275 patients.

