*Statistical Methods:* Descriptive statistics of T0, T1 and T2 values, of all the collected variables as well as the relevant changes from baseline will be presented as mean, and standard deviations, along with median values and ranges. The primary endpoint (change of TSQM-9 convenience domain at week 12) will be analyzed by a repeated measures analysis of variance adjusted for baseline factors (age, sex, disease duration, previous treatment duration, EDSS). The same technique will be adopted also for the analysis of the other endpoints. Correlations between variables will be assessed through the Spearman rank correlation coefficient.

*Interim Analysis:* No interim analysis will be performed.

*Sample Size Determination:* Data for estimating the sample size were derived from studies reporting the distribution (mean value and standard deviation) of the TSQM-9 in MS patients treated with IFN (9). Assuming an average value of the overall convenience domain at baseline of 55 (SD=16), 250 subjects allow a power of 90% to detect a change of 3 points on the overall convenience domain (from 55 to 58) under the conservative hypothesis of a SD=16 for the difference between baseline and week 12.

However, by assuming a drop-out rate up to 10% during the study, we consider it appropriate to enrol a total of 275 patients.

CONFIDENTIAL

The information contained herein may not be used, disclosed, or published without the written consent of Biogen Italia

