### **16.3.2. General Methods of Analysis**

The primary and secondary endpoints will be evaluated using a repeated measures ANOVA. The repeated measures ANOVA is used to compare group means on a dependent variable across repeated measurements of time. This statistical method is used for making simultaneous comparisons between two or more means of two or more related, not independent, groups.

However, in addition, it could be useful to apply a general linear mixed model that models for group means as fixed effects while simultaneously modeling for individual subject variables as random effects (12).

This kind of model is a subject-specific model and is a choice for analysing longitudinal data.

Unlike the repeated measures ANOVA, which requires a complete balanced array of data, the mixed model can accommodate a dataset with a large portion missing. Although the repeated measures ANOVA requires a fixed time schedule among all individual units, the mixed model can accommodate flexible time schedules. Furthermore, rather than treating time as a categorical variable, as in the repeated measures ANOVA, the mixed model is capable of treating time as either a continuous variable or a categorical variable or both.

Spearman's correlation coefficient measures the strength of association between two ranked variables.

Differences will be considered statistically significant if the p-value will be less or equal to a type I error =0.05 (two-sided test).

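### The stated 90% power does not match the plan's own two-sided 0.05 test: 250 patients, a 3-point change and SD 16 give 84%, and 90% only if the test is one-sided.

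*Protocol*

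**What the plan says.** Protocol section 16.5 takes a baseline convenience mean of 55 and states that "with 250 subjects we have a power of 90% to detect a change of 3 points", "under the conservative hypothesis of a SD=16 (9) for the difference between baseline and week 12". The synopsis has the matching sentence, "250 subjects allow a power of 90% to detect a change of 3 points", and SAP section 6 repeats section 16.5. None of the three gives an alpha level or says whether the test is one- or two-sided.

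The significance rule is in Protocol section 16.3.2: a difference counts as significant if the "p-value will be less or equal to a type I error =0.05 (two-sided test" applies. SAP section 10 has the same rule. Neither document makes an exception for the primary endpoint.

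On losses, section 16.5 adds: "by assuming a drop-out rate up to 10% during the study, we consider it appropriate to enrol a total of 275 patients".

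**The concern.** The design is single-arm and the primary endpoint is a within-patient change, so the calculation is a one-sample (paired) one. The number of patients, the effect and the SD of the difference are all given. Only alpha and sidedness are missing from the sample size paragraph, and the methods section supplies both. The power can therefore be checked directly, and it comes out about six percentage points below the stated value.

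Power is the design figure that readers use to interpret a null or borderline result. If it stands, the trial will be described, including in the publication that the SAP foresees, as having a 10% chance of missing a 3-point change when its own inputs give 16%.

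**Working it through.** **Inputs**

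- Evaluable patients: 250 (Protocol 16.5, synopsis, SAP 6)
- Change to detect: 3 points (same places)
- SD of the baseline to week 12 difference: 16 (same places)
- Test: 0.05, two-sided (Protocol 16.3.2, SAP 10)
- Enrolled: 275, with drop-out up to 10% (Protocol 16.5, synopsis, SAP 6)

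**Noncentrality**

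change / (SD / √n) = 3 / (16 / √250) = 0.1875 × 15.81 = 2.965

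**Reproducing the plan's 90%**

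With a one-sided 0.05 test, the normal approximation gives Φ(2.965 − 1.645) = Φ(1.320) = 0.9065. The noncentral t with 249 degrees of freedom gives 0.905. The smallest n for 90% is [(1.645 + 1.282) × 16/3]² = 243.6, so 244, or 245 with the t distribution. Both lie just under the planned 250, which suggests a one-sided calculation. That is an inference; the documents do not say so.

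**Power under the rule the plan states**

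With a two-sided 0.05 test, the normal approximation gives Φ(2.965 − 1.960) = Φ(1.005) = 0.8425. The noncentral t gives 0.840. A repeated measures F test with two time points is the same test and also gives 0.840.

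| Evaluable n | Two-sided 0.05 | One-sided 0.05 |
|---|---|---|
| 247 (275 less 10%) | 83.5% | 90.2% |
| 250 | 84.0% | 90.5% |
| 275 (no loss) | 87.3% | 92.7% |

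(Noncentral t.)

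**What two-sided 90% would take**

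- Patients: [(1.960 + 1.282) × 16/3]² = 298.9, so 299, or 301 with the t distribution. Allowing for 10% loss, 301 / 0.9 = 334.4, so 335 enrolled.
- Or, with 250 patients, a larger change: 3.2415 × 16 / √250 = 3.28 points (3.29 with the t distribution).
- Or, with 250 patients and 3 points, a smaller SD of the difference: 3 × √250 / 3.2415 = 14.6.

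**Type II error**

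1 − 0.840 = 0.160 against 0.10 stated, a ratio of 1.6.

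**Drop-out allowance**

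250 × 1.10 = 275 is the figure used. To keep 250 after losing 10% takes 250 / 0.90 = 277.8, so 278. From 275, a 10% loss leaves 275 × 0.90 = 247.5.

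**Other tests tried at two-sided 0.05 and n = 250**

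A signed-rank test (efficiency 0.864 to 0.955 relative to the t test) gives 78% to 82%. A three-visit overall F test, assuming equal correlation between visits, gives 76% to 87% depending on the week 24 mean. None reaches 90%.

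**The case against.** The arithmetic is not in dispute. The case on the other side has four parts.

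1. *The SD may be smaller than 16.* The plan calls 16 conservative, and the primary analysis adjusts for baseline factors. If the SD were 16 at each visit and the correlation between visits 0.6 (an assumption), the SD of the difference would be 14.3 and two-sided power 91%. But the 90% is claimed explicitly at 16, and the documents give neither a correlation nor a figure for any gain from adjustment. Reaching 90% needs an SD of 14.6, about one sixth less variance. A hoped-for smaller SD cannot support a statement made conditional on 16.

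2. *The inputs are themselves doubtful.* Entry requires a convenience score below 58. On the SAP's scoring formula the highest attainable score below 58 is 10/18 × 100 = 55.6, so a baseline mean of 55 with SD 16 cannot describe the enrolled patients. This is fair. It means that 84% is the correct result of the stated inputs, not a forecast for this trial. It does not restore the 90%.

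3. *247 evaluable is a worst case.* The drop-out allowance is an upper bound over 24 weeks, and patients lost after week 12 still have the primary measurement. This stands: evaluable numbers from 247 to 275 are possible, with power from 83.5% to 87.3%. The whole range is below 90%.

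4. *84% is still reasonable power, and nothing is biased.* Also true. It is a reason to choose the cheap correction, not to leave a wrong figure in three places.

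**Conclusion.** The concern holds. At the plan's two-sided 0.05, the stated 250 patients, 3-point change and SD of the difference of 16 give 84.0% power, not 90%. The type II error is 16%, 1.6 times the stated value. For these inputs the 90% is obtained only with a one-sided 0.05 test. The drop-out slip is secondary: it costs about half a percentage point, 84.0% to 83.5%, and only if the full 10% is lost before week 12.

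The conclusion assumes a paired comparison of week 12 with baseline and takes the plan's SD of 16 as given. Type I error and the estimate of change are not affected.

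**What to change.** Correct Protocol section 16.5, the synopsis and SAP section 6 together. State alpha and sidedness in the paragraph itself, and replace the power claim with text such as:

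> Using a two-sided test at the 0.05 level and assuming an SD of 16 for the week 12 change, 250 evaluable patients provide 84% power for a mean change of 3 points; the change detectable with 90% power is 3.3 points. If 10% of the 275 enrolled patients are lost before week 12, about 247 remain evaluable and power is 83.5%.

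This is wording only. It needs no extra patients, visits or change of analysis, and the cost is a slightly less favourable power figure. If the sponsor prefers to keep 90% at two-sided 0.05 under the same inputs, the alternative is 301 evaluable patients, about 335 enrolled with a 10% loss. Moving to a one-sided test merely to rescue the figure would contradict the significance rule in both documents.

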## **17. ETHICAL REQUIREMENTS**

Biogen Italia and the Investigator must comply with all instructions, regulations, and agreements in this protocol and applicable International Conference on Harmonisation (ICH) and Good Clinical Practice (GCP) guidelines and conduct the study according to local regulations.

### **17.1. Declaration of Helsinki**

The Investigator and Biogen Italia must adhere to the principles set forth by the Declaration of Helsinki dated October 2013.

### **17.2. Ethics Committee**

The Investigator must obtain ethics committee approval of the protocol, ICF, and other required study documents prior to starting the study.

If the Investigator makes any changes to the ICF, Biogen Italia must approve the changes before the ICF is submitted to the ethics committee. A copy of the approved ICF must be provided to Biogen Italia. After approval, the ICF must not be altered without the agreement of the relevant ethics committee and Biogen Italia.

It is the responsibility of the Principal Investigator(s) to ensure that all aspects of institutional review are conducted in accordance with current governmental regulations.

Biogen Italia must receive a letter documenting ethics committee approval, which specifically identifies the protocol, protocol number, and ICF, prior to the initiation of the study. Protocol amendments will be subject to the same requirements as the original protocol.

A progress report must be submitted to the ethics committee at required intervals and not less than annually.

At the completion or termination of the study, the investigational site must submit a close-out letter to the ethics committee and Biogen Italia.

### **17.3. Subject Information and Consent**

Prior to performing any study-related activities under this protocol, including screening tests and assessments, written informed consent with the approved ICF must be obtained from the subject or subject's legally authorized representative, as applicable, in accordance with local practice and regulations. Written informed consent must be obtained from all subjects participating in a clinical study conducted by Biogen Italia.

The background of the proposed study, the procedures, the benefits and risks of the study, and that study participation is voluntary for the subject must be explained to the subject. The subject must be given sufficient time to consider whether to participate in the study.

A copy of the ICF, signed and dated by the subject, must be given to the subject. Confirmation of a subject's informed consent must also be documented in the subject's medical record prior to any testing under this protocol, including screening tests and assessments.

Each consent form should contain an authorization allowing the Principal Investigator(s) and Biogen Italia to use and disclose PHI (i.e., subject-identifiable health information) in compliance with local law.

The signed consent form will be retained with the study records.

#### **17.4. Subject Data Protection**

Prior to any testing under this protocol, including screening tests and assessments, candidates must also provide all authorizations required by local law.

The subject will not be identified by name in the CRF or in any study reports, and these reports will be used for research purposes only. Biogen Italia, its partner(s) and designee(s), ethics committees, and various government health agencies may inspect the records of this study. Every effort will be made to keep the subject's personal medical data confidential.

#### **17.5. Compensation for Injury**

Biogen Italia maintains appropriate insurance coverage for clinical trials and will follow applicable local compensation laws.

#### **17.6. Conflict of Interest**

The Investigators should address any potential conflicts of interest (e.g., financial interest in the Sponsor) with the subject before the subject makes a decision to participate in the study.

#### **17.7. Registration of Study and Disclosure of Study Results**

Biogen Italia will register the study and post study results regardless of outcome on a publicly accessible website in accordance with the applicable laws and regulations.

## **18. ADMINISTRATIVE PROCEDURES**

### **18.1. Study Site Initiation**

The Investigator must not screen any subjects prior to completion of a study initiation visit, conducted by Biogen Italia or designee. This initiation visit will include a detailed review of the protocol and study procedures.

### **18.2. Quality Assurance**

During and/or after completion of the study, quality assurance officers named by Biogen Italia or the regulatory authorities may wish to perform on-site audits. The Investigator will be expected to cooperate with any audit and to provide assistance and documentation (including source data) as requested.

### **18.3. Monitoring of the Study**

The Principal Investigator(s) must permit study-related monitoring by providing direct access to source data and to the subjects' medical histories.

The Clinical Monitor(s) will visit the Investigator(s) at regular intervals during the course of the study and after the study has completed, as appropriate.

During these visits, CRFs and supporting documentation related to the study will be reviewed and any discrepancies or omissions will be resolved.

CRFs will be used as source data for data collected through questionnaires and scales administered to the subjects, whether filled in by the patient using the i-PAD or paper format.

The monitoring visits must be conducted according to the applicable ICH and GCP guidelines to ensure protocol adherence, quality of data, study treatment accountability, compliance with regulatory requirements, and continued adequacy of the investigational site and its facilities.

### **18.4. Study Funding**

Biogen Italia Srl is the Sponsor of the study and is funding the study. All financial details are provided in the separate contract(s) between the institution, Investigator, CRO and Biogen Italia.

### **18.5. Publications**

Details are included in the clinical trial agreement for this study.

## **19. FURTHER REQUIREMENTS AND GENERAL INFORMATION**

### **19.1. External Contract Organizations**

#### **19.1.1. Contract Research Organization**

A CRO will be responsible for administrative aspects of the study including, but not limited to, study initiation, monitoring, and management of SAE reports and data management. Before subjects are screened at each study site, the CRO will review study responsibilities with the Investigators and other study site staff, as appropriate.

#### **19.1.2. Interactive Web Response System**

The WebEZ IWRS system provided by [REDACTED] will be used in this study. Before subjects are screened or enrolled, [REDACTED] will provide each study site with appropriate training and a user manual.

#### **19.1.3. Electronic or Remote Data Capture**

Subject information will be captured and managed by study sites on electronic CRFs by a web-based electronic data capture (EDC) tool developed and supported by the CRO - [REDACTED] and configured by Biogen Italia.

### **19.2. Study Committees**

Not applicable.

### **19.3. Changes to Final Study Protocol**

All protocol amendments must be submitted to the ethics committee and Regulatory Authorities if required by local law. Protocol modifications that affect subject safety, the scope of the investigation, or the scientific quality of the study must be approved by the ethics committee before implementation of such modifications to the conduct of the study. If required by local law, such modifications must also be approved by the appropriate regulatory agency prior to implementation.

However, Biogen Italia may, at any time, amend this protocol to eliminate an apparent immediate hazard to a subject. In this case, the appropriate regulatory authorities will be notified subsequent to the modification.

In the event of a protocol modification, the subject consent form may require similar modifications (see Sections 17.2 and 17.3).

### **19.4. Ethics Committee Notification of Study Completion or Termination**

Where required, the Health Authorities and ethics committees must be notified of completion or termination of this study, and sent a copy of the study synopsis in accordance with necessary timelines.

### **19.5. Retention of Study Data**

The minimum retention time for study records will meet the strictest standard applicable to that site, as dictated by any institutional requirements or local laws or regulations. Prior to proceeding with destruction of records, the Investigator must notify Biogen Italia in writing and receive written authorization from Biogen Italia to destroy study records. In addition, the Investigator must notify Biogen Italia of any changes in the archival arrangements including, but not limited to, archival at an off-site facility or transfer of ownership if the Investigator leaves the site.

### **19.6. Study Report Signatory**

Biogen Italia will designate one of the participating Study Investigators as a signatory for the study report. This determination will be made by several factors, including, but not limited to, the Investigator's experience and reputation in the studied indication, the Investigator's contribution to the study in terms of design, management, and/or subject enrollment, or by other factors determined to be relevant by Biogen Italia.

## **22. APPENDICES:**

[figure not shown]
- Appendix A EDSS: Expanded Disability Status Score
- Appendix B TSQM9: Abbreviated Treatment Satisfaction Questionnaire to Medication
- Appendix C Treatment Adherence Assessment
- Appendix D MSTCQ: Adapted Sclerosis Treatment Concerns Questionnaire
- Appendix E MusiQol: Multiple Sclerosis International Quality of Life questionnaire
- Appendix F FSS: Fatigue Severity Scale
- Appendix G Biogen Medically Significant Terms List

CONFIDENTIAL

The information contained herein may not be used, disclosed, or published without the written consent of  
Biogen Italia

[figure not shown]

**Appendix A Expanded Disability Status Score (EDSS) (Kurtzke)**

CONFIDENTIAL

[figure not shown]
The information contained herein may not be used, disclosed, or published without the written consent of  
Biogen Italia

CONFIDENTIAL

[figure not shown]
The information contained herein may not be used, disclosed, or published without the written consent of  
Biogen Italia

**Appendix B TSQM9: Abbreviated Treatment Satisfaction Questionnaire to Medication**

[figure not shown]
CONFIDENTIAL

The information contained herein may not be used, disclosed, or published without the written consent of  
Biogen Italia

CONFIDENTIAL

[figure not shown]
The information contained herein may not be used, disclosed, or published without the written consent of  
Biogen Italia

CONFIDENTIAL

The information contained herein may not be used, disclosed, or published without the written consent of  
Biogen Italia

**Appendix C Treatment Adherence Assessment**

CONFIDENTIAL

The information contained herein may not be used, disclosed, or published without the written consent of  
Biogen Italia

CONFIDENTIAL

The information contained herein may not be used, disclosed, or published without the written consent of Biogen Italia

[figure not shown]

CONFIDENTIAL

The information contained herein may not be used, disclosed, or published without the written consent of  
Biogen Italia

[figure not shown]

**Appendix D MSTCQ: Adapted Sclerosis Treatment Concerns Questionnaire**

[figure not shown]
CONFIDENTIAL

The information contained herein may not be used, disclosed, or published without the written consent of  
Biogen Italia

[figure not shown]
CONFIDENTIAL

The information contained herein may not be used, disclosed, or published without the written consent of  
Biogen Italia

[figure not shown]
CONFIDENTIAL

The information contained herein may not be used, disclosed, or published without the written consent of  
Biogen Italia

[figure not shown]
CONFIDENTIAL

The information contained herein may not be used, disclosed, or published without the written consent of  
Biogen Italia

[figure not shown]
CONFIDENTIAL

The information contained herein may not be used, disclosed, or published without the written consent of  
Biogen Italia

CONFIDENTIAL

The information contained herein may not be used, disclosed, or published without the written consent of  
Biogen Italia

CONFIDENTIAL

[figure not shown]
The information contained herein may not be used, disclosed, or published without the written consent of  
Biogen Italia

CONFIDENTIAL

The information contained herein may not be used, disclosed, or published without the written consent of  
Biogen Italia

[figure not shown]

CONFIDENTIAL

[figure not shown]
The information contained herein may not be used, disclosed, or published without the written consent of  
Biogen Italia

**Appendix D MSTCQ: Adapted Sclerosis Treatment Concerns Questionnaire**

[figure not shown]
CONFIDENTIAL

The information contained herein may not be used, disclosed, or published without the written consent of  
Biogen Italia

[figure not shown]

**Appendix F - FSS Fatigue Severity Scale**

CONFIDENTIAL

The information contained herein may not be used, disclosed, or published without the written consent of  
Biogen Italia

